Revised Protocol 02	01-Sep-2017	Clarification of allowable contraceptives for WOCBP, addition of chronic nitrates use criteria, clarification of IP preparation, handling and storage
Administrative Letter 02	12-Jul-2017	Clarification of IP formulation as vials or ampules.
Administrative Letter 01	05-Jul-2017	Clarification of follow-up phone call 30 days after the end of the infusion of the last period (will assess occurrence of any SAEs)
Revised Protocol 01	14-Jun-2017	Inserted additional text into Section 8.1: 'Discontinuation from Study Treatment' to allow the patient to be part of the IP continuation discussion when confirmed pregnant.
Original Protocol	22-May-2017	Not Applicable

OVERALL RATIONALE FOR REVISED PROTOCOL 05:

The rational for updating this protocol is that the current version of [Appendix 3](#) directs that disease-related events do not meet the AE definition and, therefore, should not be reported as AEs. The update is part of a larger effort to harmonize AE definitions in BMS clinical studies and more particularly to allow reporting of any type of disease-related events.

SUMMARY OF KEY CHANGES FOR REVISED PROTOCOL 05		
Section Number & Title	Description of Change	Brief Rationale
Appendix 3	Updated Appendix 3 to clarify the collection of disease related events.	
The current version directs that disease-related events do not meet the AE definition and, therefore, should not be reported as AEs.
 
Unnecessary text was deleted to clarify that disease related events and events associated with lack of efficacy will need to continue to be reported as AEs if the event meets the criteria of an AE while text was added to clarify the need to report abnormal lab tests or other safety assessments when the final diagnosis is not available.
 
Content was added to clarify the need for the investigator to report the specific term of “intentional overdose” as an AE term.
 
The change is part of a larger effort to harmonize AE definitions in BMS clinical studies and more particularly to allow reporting of any type of disease-related events.

Summary	Clarified the enrollment numbers were approximately 42 participants	Brought the enrollment number estimates to align with other sections of the protocol.
Section 5.1	Clarified the enrollment numbers were approximately 42 participants	Brought the enrollment number estimates to align with other sections of the protocol.

9.6 Pharmacodynamics	54
9.7 Pharmacogenomics	54
9.7.1 ADME Sampling	54
10 STATISTICAL CONSIDERATIONS	55
10.1 Sample Size Determination.....	55
10.2 Populations for Analyses	56
10.3 Statistical Analyses	56
10.3.1 Efficacy Analyses	57
10.3.2 Safety Analyses	57
10.3.3 Other Analyses	57
10.3.4 Pharmacokinetic Analyses	57
10.3.5 Interim Analyses	57
12 APPENDICES	62
APPENDIX 1 ABBREVIATIONS AND TRADEMARKS	63

APPENDIX 2 STUDY GOVERNANCE CONSIDERATIONS	66
APPENDIX 3 ADVERSE EVENTS AND SERIOUS ADVERSE EVENTS: DEFINITIONS AND PROCEDURES FOR RECORDING, EVALUATING, FOLLOW UP AND REPORTING.....	73
APPENDIX 4 WOMEN OF CHILDBEARING POTENTIAL DEFINITIONS AND METHODS OF CONTRACEPTION.....	78

Objectives and Endpoints:

Table 1-1: Objectives and Endpoints

Objectives	Endpoints
Primary 
Evaluate the effects of BMS-986231 on the left ventricular (LV) systolic function by stroke volume index (SVI) assessed by echocardiography compared to placebo.	
Mean SVI derived from the velocity time integral at the left ventricular outflow tract (LVOT VTI) at the end of the 5-hours infusion of BMS-986231, versus placebo.
Secondary 
Evaluate the effects of BMS-986231 on the left ventricular (LV) systolic function by stroke volume index (SVI) assessed by echocardiography compared to nitroglycerin (NTG).Evaluate the effects of BMS-986231 on selected other left ventricular systolic and diastolic indices compared to placebo and NTG	
Mean SVI derived from LVOT VTI at the end of the 5-hours infusion of BMS-986231, versus NTG.Mean LVEF, computed by Simpson's method at the end of the 5-hours infusion of BMS-986231, versus placebo and NTG.Mean cardiac power index at the end of the 5-hours infusion of BMS-986231, versus placebo and NTG.Mean Diastolic indices: E/A, annular e' velocity and E/e' ratio at the end of the 5-hours infusion of BMS-986231, versus placebo and NTG.Mean LV global longitudinal strain, computed using STE at the end of the 5-hours infusion of BMS-986231, versus placebo and NTG.

Overall Design:

This is a multi-center, randomized, cross-over, placebo and active-controlled, double-blind, study of continuous 5-hour intravenous (IV) infusion of BMS-986231 in patients with heart failure and reduced ejection fraction (HFrEF). The trial is designed to evaluate the effects of BMS-986231 on systolic and diastolic parameters measured by echocardiography.

Design

A cross-over design will be implemented in this trial, every subject will be exposed to each of the 3 interventions in 3 treatment periods (BMS-986231, NTG and placebo) with one intervention occurring during each treatment period, including the 5-hour infusion, followed by a washout period of at least 5 days, but no more than 4 weeks.

Study drug

Approximately 42 study participants will be randomized to receive BMS-986231, NTG, and placebo, in one of the 6 possible sequences.

NTG, BMS-986231 and placebo: will be administered as a 5-hours infusion according to an up-titration schedule, which is achieved by an increase in the infusion flow rate. All three interventions

(NTG, BMS-986231 and placebo) will have the same flow rate as follows: 5 mL/H for 10 min, followed by 10 mL/H for 10 minutes then 20 mL/H for the rest of the infusion.

The corresponding doses of the active study medications will be:

- NTG: 20 µg/min for 10 min, followed by 40 µg/min for 10 min, followed by 80 µg/min for the rest of the 5-hour infusion;
- BMS-986231: 3 µg/kg/min for 10 min, followed by 6 µg/kg/min for 10 min, followed by 12 µg/kg/min for the rest of the 5-hour infusion.

In case of decrease in systolic blood pressure, an algorithm will be used to down-titrate / interrupt or discontinue the study drug infusion (see [section 7.4](#) in the protocol).

Screening

Screening for inclusion in the study will be performed up to 4 weeks before the first treatment day. Screening will assess the eligibility criteria including assessment of ejection fraction, suitability of echocardiography windows and image quality. After screening, study participants will be enrolled in the study according to their eligibility as per the inclusion and exclusion criteria, and will be randomized to 1 of the 6 sequences that will be conducted in parallel.

If the period 1 treatment day could only be scheduled beyond 4 weeks from screening, a consultation with the medical monitor is needed to identify which screening procedure should be repeated prior to randomization.

Treatment day (Day 1 of each period)

Study participants will be admitted to the study facility on the treatment day, which will be the Day 1 of each of the three periods. Assessment of vital signs and laboratory tests will be performed pre-dose. In each treatment day, blood pressure and heart rate should be within the inclusion / exclusion criteria limits, and no atrial fibrillation or atrial flutter should be present in order to start the study treatment. The study drug infusion could start without waiting for the results of the laboratory assessments done in the morning of the treatment day at the study facility if the following criteria are met:

- The results of the laboratory assessment at screening / previous period are within ranges compatible with inclusion/exclusion criteria,
- The study participant was medically stable without change in medication since the screening visit / previous period.

If the laboratory tests (e.g. electrolytes, serum creatinine, eGFR, hemoglobin, transaminases) prior to infusion, are not within inclusion and exclusion criteria limits, the study drug will be discontinued after consultation with the medical monitor. The abnormalities should be corrected before the next treatment period.

Physical examinations, vital sign measurements, 12-lead electrocardiograms (ECG), echocardiography, whole body bioimpedance and pulse wave analysis (non-invasive central aortic blood pressure) will be performed at selected times throughout the dosing interval. Participants

[figure not shown]
will be closely monitored for adverse events throughout the study. Blood samples will also be collected at selected intervals after the start of study drug administration for pharmacokinetic (PK) analysis.

Discharge

Study participants will remain in the study facility for approximately 3.5 hours post-dose and discharged on the same day, unless the investigator and the study team consider that an overnight stay is warranted. Same-day discharge is allowed if the following conditions are met:

- in the opinion of the investigator an overnight stay is not warranted,
- there is no hypotension after mobilization and
- none of the following events occurred during the study drug infusion: prolonged hypotension, symptoms of hypotension, new onset of sustained arrhythmia requiring pharmacologic or other interventions, any other events of concern e.g. chest pain suggestive of ischemia.

Figure 1: Study design

***Wash-out period will be at least 5 days, but no more than 4 weeks.**

Number of Participants:

Sample sizes are calculated based on comparison of post-baseline values, adjusting for the differences in the baseline value. Sample size calculations assume an increase of the stroke volume index (SVI) of 4.5 mL/m² from baseline, relative to placebo, an inter-individual SD of 10 mL/m²,

and intra-individual correlations for the difference between assessments of 0.7. Approximately 36 subjects with data from treatment periods being compared will be required to achieve a power of 90%, with a type I error probability of 0.05 (2-sided). In order to address the potential for missing data arising from withdrawal from the study, an allowance of approximately 15% subjects will be included, with a resulting target sample size of 42 subjects to be randomized. An estimated 42 subjects will be randomized, in order to complete 36 subjects.

Randomized: 42

Key Inclusion / Exclusion Criteria:

Inclusion:

- Signed Written Informed Consent
- Age 18 years (or age of majority) or older
- Heart failure with reduced ejection fraction (LVEF on echocardiogram of 40% or less), as assessed by the echocardiographic core lab.
- Stable guideline directed therapy for heart failure (could include oral diuretics, ACEi, ARBs, ARNi, MRAs, and β blockers as tolerated), with no dose changes of these medications in the past 2 weeks
- Have screening values of NT pro-BNP \geq 125 pg/mL (15 pmol/L) or BNP \geq 35 pg/mL (10 pmol/L).
- In sinus rhythm at the start of the infusion

Exclusion:

- Body weight $<$ 45 kg or \geq 140 kg
- Low quality echocardiographic visualization windows and image acquisition
- Systolic blood pressure (SBP) $<$ 110 mm Hg at screening or pre-randomization
- Heart rate $<$ 50 beats per minute (bpm) or $>$ 90 bpm at screening or pre-randomization
- Permanent Atrial Fibrillation, Atrial Flutter or having Atrial Fibrillation, Atrial Flutter before start of the infusion
- Permanent paced rhythm (VVI, DDD or BiV pacing)
- Ventricular assist device or prior heart transplant
- Primary HF etiology attributable to either restrictive/obstructive cardiomyopathy, idiopathic hypertrophic or uncorrected severe valvular disease as defined by AHA/ACC/ESC criteria.
- (Note: A restrictive mitral inflow pattern is NOT exclusionary)
- Large post-MI Left Ventricular aneurisms
- Intra-cardiac thrombus
- Prior mitral valve repair, mitral or aortic prosthesis

- Treatment with oral phosphodiesterase type 5 (PDE5) inhibitor sildenafil, vardenafil or avanafil within 24 hours of study drug infusion or treated with tadalafil within 4 days of study drug infusion
- Hospitalized for acute decompensated heart failure in the previous month
- Hospitalized with acute coronary syndrome, coronary revascularization or acute myocardial infarction during the previous 90 days prior to screening
- Have a history of a cerebral vascular accident (CVA or stroke) or of a transient ischemic attack (TIA) during the previous 90 days prior to screening
- NYHA Class IV symptoms of heart failure
- Treatment with intravenous inotropic therapy (dobutamine, milrinone, levosimendan) in the previous month or planned treatment in the next 3 months.
- Current treatment with chronic oral, transdermal or sublingual nitrates, except at the discretion of the investigator and treating physician, nitrates could be temporarily interrupted. In which case, an interruption of 3 days is required prior to start of study drug.
- Prior solid organ transplant
- Estimated glomerular filtration rate (eGFR) < 15 ml/min/1.73 m²
- Have persistent abnormal serum electrolytes not resolved between screening and start of the study drug infusion, as defined by any of the following:
 - A sodium (Na⁺) concentration < 130 or > 145 mEq/L (mmol/L)
 - A potassium (K⁺) concentration < 3.2 or > 5.5 mEq/L (mmol/L)
- Have severe anemia, as documented by a hemoglobin < 9 g/dL (< 5.59 mmol/L)
- Liver disease defined as history of cirrhosis with evidence of portal hypertension such as varices, or encephalopathy, or total bilirubin > 3 mg/dL (> 51 µmol/L) or significant elevation of liver enzymes (AST, ALT > 3 times the upper limit of normal)
- Considered clinically unstable for any condition
- Serious comorbid non cardiovascular disease in which the life expectancy of the subject is < 3 months
- Known hypersensitivity or contra-indication to the intravenous echocardiography contrast agent, in case contrast echocardiography is used

2 SCHEDULE OF ACTIVITIES

Table 2-1: Time & Event Schedule CV013020, Screening Period

Procedure	Screening Visit	Notes
Eligibility Assessments		
Informed Consent	x	A participant is considered enrolled only when a protocol specific informed consent is signed.
Inclusion/Exclusion Criteria	x	
Medical History	x	
Concomitant medications	x	
Echocardiography eligibility assessment	x	As described in the echocardiographic core lab manual, evaluation of image quality and assessment of ejection fraction
Safety Assessments		
Physical Examination	x	If the screening physical examination is performed within 3 days prior to first dosing then a single exam may count as both the screening and pre-dose evaluation. Includes height and weight.
Vital Signs	x	Includes body temperature, respiratory rate, and seated blood pressure and heart rate. Blood pressure and heart rate should be measured after the participant has been resting quietly for at least 5 minutes.
Adverse Events Assessment	x	SAEs must be collected from the date of the participant's Informed consent.
Local Laboratory Tests	x	Hematology, Serum chemistry, NT-proBNP or BNP (details in the protocol section 9.4.4)
Pregnancy Test (WOCBP only)	x	

Table 2-2: Time & Event Schedule CV013020, Treatment and Follow-up Study Periods

Procedure	Treatment Period					Notes
	Period 1 Day 1	Washout 5-28 Days	Period 2 Day 1	Washout 5-28 Days	Period 3 Day 1	
Safety Assessments						Washout between periods should be at least 5 days and no more than 4 weeks.
Weight	x		x		x	Weight pre-and end of the infusion in each treatment period.
Targeted physical examination	x		x		x	Based on subject's report since the screening visit. Includes temperature, signs and symptoms of congestion.
Vital Signs (Blood pressure and heart rate)	x		x		x	Prior to infusion. 30 minutes at first hour, then every 1 hour until discontinuation of infusion, then at 1 hour, 2 hour and 3.5 hour after end of infusion in each treatment period.
Peripheral Oxygen Saturation	x		x		x	Prior and end of the infusion in each treatment period, measured with a pulse oximeter device.
12 lead ECG	x		x		x	Prior to the infusion and after end of infusion in each treatment period.
Urinary output	x		x		x	From start of infusion to 3 hours after end of infusion in each treatment period.
Telemetry	x		x		x	From start of infusion to 3 hours after end of infusion in each treatment period.
Adverse Events Assessment				x		Non-serious AEs will be collected from the start of the study drug infusion, until 24 hours after end of infusion in each treatment period of dosing in each period
					x	Serious adverse events must be collected from the date of Informed consent and will be assessed up to 30 days after the end of infusion of the last period.

Table 2-2: Time & Event Schedule CV013020, Treatment and Follow-up Study Periods

Procedure	Treatment Period					Notes
	Period 1 Day 1	Washout 5-28 Days	Period 2 Day 1	Washout 5-28 Days	Period 3 Day 1	
Concomitant Medications	x		x		x	Chronic heart failure medications to be taken during the treatment day (D1 of each period) will be withheld until the end of the study drug infusion in each treatment period.
Follow-up call	x		x		x	Follow-up call to be done at Day 2 of each period (will inquire about general status and occurrence of any AEs) and 30 days after the end of the infusion of the last period (will assess occurrence of any SAEs).
Local Laboratory Tests	x		x		x	Hematology and Serum chemistry (details in the protocol section 9.4.4). Can be performed within 24 hours of treatment day.
Central Laboratory Tests	x		x		x	Hematology, Serum chemistry, Biomarkers (details in the protocol section 9.4.4)
Pharmacokinetic (PK) sampling	x		x		x	PK sampling will be done pre-dose, 0.5 hour, 1 hour, 4.5 hours and 7 hours after the start of the infusion in each treatment period. In addition, PK samples should be taken when the dose is lowered or in case of early discontinuation (see protocol section 9.5)
Pregnancy Test (WOCBP only)	x		x		x	Can be performed within 24 hours of treatment day.
Efficacy Assessments						
Echocardiography	x		x		x	Prior to and before the end of the study infusion (between hour 4 and hour 5) in each treatment period. If study drug is interrupted prematurely, the echocardiography assessment should be done as soon

Table 2-2: Time & Event Schedule CV013020, Treatment and Follow-up Study Periods

Procedure	Treatment Period					Notes
	Period 1 Day 1	Washout 5-28 Days	Period 2 Day 1	Washout 5-28 Days	Period 3 Day 1	
						Washout between periods should be at least 5 days and no more than 4 weeks.
						as possible after study drug interruption. If the study drug is resumed after interruption, echocardiography should be repeated between hour 4 and hour 5 of the effective study drug infusion.
Whole body bioimpedance	x		x		x	Prior to infusion, at 1 hour and 3 hours after start of infusion, at end of infusion and 2 hours after the end of the infusion in each treatment period. In addition, should be performed after each supplementary echocardiographic assessment.
Pulse wave analysis	x		x		x	Prior to and at end of infusion in each treatment period, just after the echocardiographic assessment has been performed. In addition, should be performed after each supplementary echocardiographic assessment.
Administer Study Medication	x		x		x	5-hour continuous infusion *Study medication to begin promptly after pre-infusion testing completed*
Clinical Drug Supplies						
Randomize	x		x		x	
Dispense Study Drug	x		x		x	
Additional Research Sampling						
Additional Research plasma	x		x		x	Sampling will be done pre-dose and 4.5 hours after the start of the infusion in each treatment period.
Blood sampling for DNA variants in mARC and ADME related genes	x					Sample can be collected at Period 1 Day 1 or any other day, only one sample collection for each subject during the study.

In the event of multiple procedures are required at a single time point, the following order for performing the procedures is recommended:

Revised Protocol No.: 05
Date: 24-Jan-2019

Approved v6.0 930114837 6.0

- Safety
- Pharmacokinetic sampling
- Additional research sampling

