5 STUDY DESIGN

5.1 Overall Design

This is a multi-center, randomized, cross-over, placebo and active-controlled, double-blind, study of continuous 5-hour intravenous (IV) infusions of BMS-986231 in patients with heart failure and reduced ejection fraction (HF_rEF). The trial is designed to evaluate the effects of BMS-986231 on systolic and diastolic parameters measured by echocardiography.

Design

A cross-over design will be implemented in this trial, every subject will be exposed to each of the 3 interventions in 3 treatment periods (BMS-986231, NTG and placebo) with one intervention occurring during each treatment period, including the 5-hour infusion, followed by a washout period of at least 5 days, but no more than 4 weeks.

Study drug

Approximately 42 study participants will be randomized to receive BMS-986231, NTG, and placebo, in one of the 6 possible sequences.

NTG, BMS-986231 and placebo will be administered as a 5-hours infusion, according to an up-titration schedule, which is achieved by an increase in the infusion flow rate. All three interventions (NTG, BMS-986231 and placebo) will have the same flow rate as follows: 5 mL/H for 10 min, followed by 10 mL/H for 10 minutes then 20 mL/H for the rest of the infusion.

The corresponding doses of the active study medications will be:

- NTG: 20 $\mu\text{g}/\text{min}$ for 10 min, followed by 40 $\mu\text{g}/\text{min}$ for 10 min, followed by 80 $\mu\text{g}/\text{min}$ for the rest of the 5-hour infusion;
- BMS-986231: 3 $\mu\text{g}/\text{kg}/\text{min}$ for 10 min, followed by 6 $\mu\text{g}/\text{kg}/\text{min}$ for 10 min, followed by 12 $\mu\text{g}/\text{kg}/\text{min}$ for the rest of the 5-hour infusion.

In case of a decrease in systolic blood pressure, an algorithm will be used to down-titrate / interrupt or discontinue the study drug infusion (see [section 7.4](#) in the protocol).

Screening

Screening for inclusion in the study will be performed up to 4 weeks before the first treatment day. Screening will assess the eligibility criteria including assessment of ejection fraction, suitability of echocardiography windows and image quality. After screening, study participants will be enrolled in the study according to their eligibility as per the inclusion and exclusion criteria, and will be randomized to 1 of the 6 sequences that will be conducted in parallel.

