If the first period of treatment day could only be scheduled beyond 4 weeks from screening, a consultation with the BMS/PPD medical monitor is needed to identify which screening procedure should be repeated prior to randomization.

Treatment day (Day 1 of each period)

Study participants will be admitted to the study facility on the treatment day, which will be the Day 1 of each of the three periods. Assessment of vital signs and laboratory tests will be performed pre-dose. In each treatment day, blood pressure and heart rate should be within the inclusion / exclusion criteria limits, and no atrial fibrillation or atrial flutter should be present in order to start the study treatment. The study drug infusion could start without waiting for the results of the laboratory assessments done in the morning of the treatment day at the study facility if the following criteria are met:

- The results of the laboratory assessment at screening / previous period are within ranges compatible with inclusion/exclusion criteria,
- The study participant was medically stable without change in medication since the screening visit / previous period.

If the laboratory tests (e.g. electrolytes, serum creatinine, eGFR, hemoglobin, transaminases) prior to the infusion, are not within inclusion and exclusion criteria limits, the study drug will be discontinued after consultation with the medical monitor. The abnormalities should be corrected before the next treatment period.

Physical examinations, vital sign measurements, 12-lead electrocardiograms (ECG), echocardiography, whole body bioimpedance and pulse wave analysis (non-invasive central aortic blood pressure) will be performed at selected times throughout the dosing interval. Participants will be closely monitored for adverse events throughout the study. Blood samples will also be collected at selected intervals after start of study drug administration for pharmacokinetic (PK) analysis.

Discharge

[figure not shown]
Study participants will remain in the study facility for approximately 3.5 hours post-dose and discharged on the same day, unless the investigator and the study team consider that an overnight stay is warranted. Same-day discharge is allowed if the following conditions are met:

- in the opinion of the investigator an overnight stay is not warranted,
- there is no hypotension after mobilization and

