The administration of the study drugs will be done through an infusion pump connected to a single peripheral IV line. After priming the infusion set tubing and connecting the lines to the intravenous catheter, the pump should be set to deliver the rates of infusion indicated on the infusion bag label according to the up-titration schedule (See [Section 5.1](#)).

The pump infusion volume display should be re-set to 0 after priming the infusion line and just prior to the start of the infusion, and the total volume infused at the conclusion of the infusion after 5-hours, or at the time of any early discontinuation, should be recorded in the clinic source documents.

[figure not shown]
At any time during the administration of study drug, the study drug infusion must be discontinued if an adverse event or any other safety issue suggests it is not in the patient's best interest to continue to receive study drug.

The investigator has the option to adjust the study drug dosage level downward by 50%, interrupt or discontinue the study drug infusion in patients that develop hypotension, or if the patient experiences symptomatic hypotension that is not easily tolerated, as follows (and shown in Figure 7.4-1)

- **Study drug reduction:** Study drug is decreased by 50% if SBP decreases to levels <90 mmHg but ≥ 80 mmHg. The dose cannot be subsequently increased.
- **Study drug interruption:** Study drug is interrupted for 1 hour if SBP decreases to <80 mmHg or symptoms of low blood pressure occur within the first 4 hours of infusion. If the SBP is ≥ 105 mmHg after one hour interruption, the study drug could be resumed at 50 % of the dose to complete 5-hours of effective study drug infusion.
- **Study drug discontinuation:** Study drug will be permanently discontinued if SBP remains < 105 mmHg after 1 hour interruption or if SBP decreases to levels <80 mmHg or symptoms of low blood pressure occur after 4 hours of infusion.

End of infusion procedures should be done as soon as possible after interruption or discontinuation of the study drug. If an infusion in a given period is discontinued, patients remain eligible to complete subsequent periods.

Figure 7.4-1: BP Management Algorithm

Any decision to lower the dosage level of study drug or discontinue study drug should be based on the investigator's assessment of the patient's overall clinical stability, in the context of appropriate ongoing monitoring of the patient's condition.

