A 50% dosage adjustment downward will be achieved by decreasing the rate of study drug infusion from 20 mL/H to 10 mL/H.

In order to ensure compatibility with BMS-986231 and NTG, the placebo solution will be D5W.

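### No on-drug blood pressure is scheduled before either infusion-rate increase (minutes 10 and 20); the first reading is at minute 30, ten minutes into full rate

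*Protocol*

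**What the plan says.** Protocol Section 5.1 gives all three treatments the same flow: "5 mL/H for 10 min, followed by 10 mL/H for 10 minutes then 20 mL/H for the rest of the infusion". Both increases are set by time alone; no blood pressure condition is attached to them.

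Table 2-2 (Section 2, Vital Signs row) has blood pressure and heart rate taken before the infusion and then "30 minutes at first hour, then every 1 hour until discontinuation of infusion". Section 9.4.2 only points back to Section 2.

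Section 7.4 sets the SBP rules:

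- Reduction: "Study drug is decreased by 50% if SBP decreases to levels <90 mmHg but ≥ 80 mmHg. The dose cannot be subsequently increased". No start time is given.
- Interruption: "Study drug is interrupted for 1 hour if SBP decreases to <80 mmHg or symptoms of low blood pressure occur", with the window running over the first 4 hours of infusion.
- How the reduction is done: "A 50% dosage adjustment downward will be achieved by decreasing the rate of study drug infusion from 20 mL/H to 10 mL/H". No other pump setting is stated.

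The same section adds a general stop rule ("the study drug infusion must be discontinued if an adverse event or any other safety issue" makes continuing unwise for the patient) and asks that dose decisions be taken "in the context of appropriate ongoing monitoring". Before each infusion there is a recheck: "In each treatment day, blood pressure and heart rate should be within the inclusion / exclusion criteria limits". Under exclusion criterion 1a that means SBP of at least 110 mmHg.

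**The concern.** A site that follows Table 2-2 exactly takes the pump from 5 to 20 mL/H, a fourfold rise, with no scheduled reading that could trigger an SBP rule. Symptoms would still stop the drug. A fall without symptoms would not be looked for by schedule before the rate is doubled, and then doubled again.

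The drugs make this relevant. Section 9.3 describes BMS-986231 as a vasodilator and names low blood pressure as possibly the first effect of an overdose. Nitroglycerin follows the same rate steps under the blind. What is at stake is the safety of individual patients in the first half hour. The gap does not bear on the validity of the primary comparison of stroke volume index.

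**Working it through.** **Inputs.** Rate steps and doses: Section 5.1 and Table 7.1-1. Reading times: Table 2-2. Planned numbers: 42 patients and 3 periods (Section 5.1), 36 completers, 90% power and a 4.5 mL/m² effect (Section 10.1). The plan gives no figure of its own on this point to reproduce.

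**1. Timeline.**

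| Minute | Event |
|---|---|
| before 0 | scheduled blood pressure; SBP at least 110 mmHg |
| 0 | 5 mL/H |
| 10 | 10 mL/H |
| 20 | 20 mL/H (full rate) |
| 30 | first scheduled on-drug blood pressure |

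The Table 2-2 wording could mean one reading at 30 minutes or a reading every 30 minutes in the first hour. The first reading falls at minute 30 either way, 30 − 20 = 10 minutes after full rate starts. Scheduled on-drug readings by minute 10: 0. By minute 20: 0. So 0 of 2 increases are covered, in all 42 × 3 = 126 planned infusions, of which 42 × 2 = 84 are active.

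**2. Other measurements.** Pulse wave analysis is done before and at the end of infusion. Bioimpedance starts at 1 hour. Telemetry runs from the start but is not described as measuring blood pressure. None fills the gap.

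**3. Do the rules reach the first 20 minutes?** The interruption rule does, because minutes 0 to 20 lie within its 4-hour window. The reduction rule names no start time, but its only stated pump change starts from 20 mL/H, so its use at the lower steps is not settled by the text.

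**4. Dose given before the first reading.**

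- BMS-986231, full: 10×3 + 10×6 + 280×12 = 3,450 µg/kg. By minute 20: 30 + 60 = 90 (2.6%). By minute 30: 90 + 10×12 = 210 (6.1%).
- Nitroglycerin, full: 10×20 + 10×40 + 280×80 = 23,000 µg. By minute 20: 200 + 400 = 600 (2.6%). By minute 30: 600 + 10×80 = 1,400 (6.1%).

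**5. What a hold would cost in dose, if it were never lifted.**

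- Held at 5 mL/H throughout: 300×3 = 900 µg/kg, or 26.1% of 3,450; rate at the hour 4 to 5 echocardiogram is 25% of target.
- Held at 10 mL/H from minute 10: 30 + 290×6 = 1,770 µg/kg, or 51.3%; rate is 50% of target.
- For comparison, a patient cut under the existing rule at minute 30: 210 + 270×6 = 1,830 µg/kg, or 53.0%; rate is also 50% of target.

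So a lasting hold at the second step ends at the same rate as the existing cut. Only a lasting hold at the first step ends lower.

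**6. Illustrative worst case for the primary contrast.** Assume that k of 36 completers are held at 5 mL/H for the whole BMS-986231 infusion and would otherwise have been at full rate, that effect is proportional to rate, and that variance is unchanged. The loss in mean effect is 4.5 × 0.75 × k/36 = 0.09, 0.19 and 0.28 mL/m² for k = 1, 2, 3. Power is Φ(3.2415 × (1 − 0.75k/36) − 1.96), where 3.2415 = 1.96 + 1.2815 reproduces the planned 90% at k = 0. The results are about 89%, 87% and 86%. The counts are assumptions; the documents give none.

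**The case against.** The strongest reply is that the cover is already reasonable. The quarter-rate start is itself a safeguard. With SBP of at least 110 mmHg before each infusion, a patient would have to drop by more than 20 mmHg, without symptoms, within 20 minutes at a quarter or half of full rate. Heart failure drugs are withheld that morning, chronic nitrates are stopped for 3 days, patients are on telemetry, and any safety issue stops the drug. In earlier studies blood pressure came back one to two hours after BMS-986231 was stopped. All of this stands. It lowers the likely harm but does not supply a reading.

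Section 7.4 also introduces its rules as choices open to the investigator and refers to ongoing monitoring, so Table 2-2 need not be the only source of readings. That is fair too, but the general wording permits an earlier reading without requiring one.

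A reader might go further and infer that a patient with SBP of 80 to below 90 mmHg on the 5 or 10 mL/H step must be halved for good, and that the protocol is at fault for not giving those pump settings. The documents do not support this. The rules are left to the investigator's judgement, and the only stated mechanic is 20 to 10 mL/H. A permanent cut at minute 10 would also leave the patient at 2.5 mL/H, 12.5% of target rate, through the primary echocardiogram. That is a debatable trade-off, not something the text plainly demands.

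Finally, Figure 7.4-1 and the Study Pharmacy Manual are not available here, and either might already set early readings. The public text of the introduction may also be incomplete, so the absence of early hypotension data cannot be held against the plan.

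**Conclusion.** The point holds as a gap in the schedule: no on-drug blood pressure is scheduled before either rate increase, although at least the interruption rule is in force at both. Its size is 0 of 2 increases covered in every infusion, with 2.6% of the dose given by the last step and 6.1% by the first reading. These are exposure figures.

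A reader might infer that patients are shown to be at material risk, or that the primary result is threatened. Neither follows. The visible documents give no frequency or onset time for early hypotension, and nothing here biases the comparison with placebo. It is a cheap improvement for patient safety that should be made.

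The conclusion assumes that Figure 7.4-1 and the Study Pharmacy Manual add no blood pressure times during titration. If either does, the change reduces to bringing Table 2-2 into line.

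**What to change.** 1. **Table 2-2, Vital Signs row:** add cuff blood pressure and heart rate immediately before the minute 10 and minute 20 rate changes.
2. **Section 7.4:** state that the rate is not stepped up while SBP is below 90 mmHg. The current step is held, and the infusion is interrupted if SBP is below 80 mmHg or symptoms occur, as already written. Make clear that a hold is not a reduction, so the bar on later increases does not apply to it, and that the 50% reduction stays with the 20 mL/H rate for which its mechanics are given.

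The same readings and hold apply to all three infusions, so the blind is unaffected.

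**Cost.** Two readings per infusion, at most 126 × 2 = 252 scheduled readings, in attended patients already on telemetry; rechecks in a held patient come on top. One table row, a short addition to Section 7.4, matching eCRF fields, and two more time points in the vital-sign summary of SAP Section 7.6.6. The real downside is that a held patient may reach full rate later or not at all.
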